## 8.7. Study size

No sample size has been calculated, as this is a characterisation and drug utilisation study with a descriptive design, which will not test a specific hypothesis. In addition, we will use already available data to describe treatment and characteristics of individuals receiving immunoglobulins. Thus, the sample size is driven by the availability of data for individuals with a prescription for prespecified immunoglobulin types and brands. Based on a preliminary feasibility assessment, the expected number of person counts for immunoglobulins in the data sources included in this study range from 10,900 (CDW Bordeaux) to 73,600 (CPRD GOLD).

## 8.8. Analysis

### 8.8.1. Federated network analyses

All analyses will be conducted separately for each data source and will be carried out in a federated manner, allowing analyses to be run locally without sharing individuals' data.

Before sharing the study package, test runs of the analytics will be performed on a subset of the data sources, and quality control checks will be performed. After all the tests are passed (see [Annex III. Operational and reporting considerations](#)), the final package will be released in a version-controlled study repository for execution against all the participating data sources.

### 8.8.2. Data privacy protection

The data partners will locally execute the analytics against the OMOP CDM in R Studio and review and approve the default aggregated results. They will then be made available to the Principal Investigators and study team in secure online repository of DTZ (Data Transfer Zone). All results will be locked and timestamped for reproducibility and transparency. The study results of all data sources will be checked, after which they are made available to the team, and the Study Dissemination Phase can start. All analyses will be conducted separately for each data source, and will be carried out in a federated manner, allowing analyses to be run locally without sharing patient-level data. Cell counts <5 will be suppressed when reporting results to comply with the data source's privacy protection regulations.

### 8.8.3. Statistical model specification and assumptions of the analytical approach considered

#### Objective 1

Trends of immunoglobulin use during the study period will be assessed based on OMOP CDM mapped data using the *IncidencePrevalence* R package (<https://github.com/darwin-eu/IncidencePrevalence>), developed by DARWIN EU®.

The prevalence of individuals with a recorded immunoglobulin prescription (expressed as the proportion of individuals with any immunoglobulin prescription in the general study population) will be presented by immunoglobulin ingredient, route of administration, and stratified by sex and age.

Prevalence will be calculated as overall and annual, which summarises the total number of individuals with recorded immunoglobulin use during a given period divided by the population at risk of receiving immunoglobulins during that period. Therefore, period prevalence will give the proportion of individuals exposed at any time during a specified interval. Binomial 95% confidence intervals will be calculated.

#### Objective 2

Trends of immunoglobulin use during the study period will be assessed based on OMOP CDM mapped data using the *IncidencePrevalence* R package (<https://github.com/darwin-eu/IncidencePrevalence>), developed by DARWIN EU®.

The quarterly prevalence of individuals with prescriptions for prespecified immunoglobulin brands will be estimated (expressed as the proportion of individuals prescribed each specific immunoglobulin brand among prevalent immunoglobulin users).

Prevalence will be calculated as quarterly period prevalence, which summarises the total number of individuals with recorded immunoglobulin brand prescription during a quarter divided by the population of prevalent immunoglobulin users during that period. Therefore, period prevalence will give the proportion of individuals exposed to a specific brand at any time during the specified interval. Binomial 95% confidence intervals will be calculated.

An illustration of the calculation of period prevalence is shown below in **Figure 3**. Between time  $t+2$  and  $t+3$ , two of the five study participants receive immunoglobulin treatment, giving a prevalence of 40%. Meanwhile, for the period  $t$  to  $t+1$  all five also had some observation time during the year with one of the five study participants having a recorded immunoglobulin prescription, giving a prevalence of 20%.

[figure not shown]

Figure 3. Prevalence example.

### Objective 3

The dose, duration of use, and number of immunoglobulin prescriptions will be calculated per prespecified immunoglobulin brand based on OMOP CDM mapped data using the *DrugUtilisation* R package (<https://github.com/darwin-eu/DrugUtilisation>), developed by DARWIN EU®.

#### Drug exposure calculations

Drug eras are defined as follows: exposure starts at the date of the first prescription of prespecified immunoglobulin brand during the study period. For primary care data sources, a washout period of 180 days will be applied prior to inclusion. For each prescription, the estimated duration of use will be retrieved from the drug exposure table in the OMOP CDM, using the recorded start and end date of the exposure. Subsequent prescriptions will be combined into continuous exposed treatment episodes (drug eras) using the following specifications: two drug eras will be merged into one continuous drug era if the distance in days between end of the first era and start of the second era is  $\leq 30$  days. The time between the two joined eras will be considered as exposed by the first era as shown in **Figure 4**, first row. The cumulative dose is the sum of defined daily doses (DDDs) multiplied by the number of days exposed to each dose, i.e., the total dose taken throughout the exposures considered in the time-window reported per prespecified immunoglobulin brand.

Gap era joint mode	Schematics	Dose in between	Cumulative dose	Cumulative time
"first"		$d_1$	$d_1 \cdot (x_1 + x_{12}) + d_2 \cdot x_2$	$x_1 + x_{12} + x_2$
"second"		$d_2$	$d_1 \cdot x_1 + d_2 \cdot (x_2 + x_{12})$	$x_1 + x_{12} + x_2$
"zero"		0	$d_1 \cdot x_1 + d_2 \cdot x_2$	$x_1 + x_{12} + x_2$
"join"	 <small>first exposure      gap      second exposure</small> <small>time = <math>x_1</math>, dose = <math>d_1</math>      time = <math>x_{12}</math>      time = <math>x_2</math>, dose = <math>d_2</math></small>	NA	$d_1 \cdot x_1 + d_2 \cdot x_2$	$x_1 + x_2$

Figure 4. Gap era joint mode.

If two exposures overlap, the overlap time will be considered exposed to the first exposure (**Figure 5**). No time will be added at the end of the combined drug era to account for the overlap. If two exposures start at the same date, the overlapping period will be considered exposed to both.

Overlap mode	Schematics	Dose overlap
"first"		$d_1$
"second"		$d_2$
"both"		$d_1 + d_2$
"maximum"		$\max(d_1, d_2)$

Figure 5. Gap era overlap mode.

The number of prescriptions, initial and cumulative dose of the index drug, as well as duration of use, will be provided per prespecified immunoglobulin brand as minimum, q25, median, q75, and maximum. For data sources where duration cannot be calculated, due to e.g., missing information on quantity or dosing, treatment duration will not be provided.

### Objective 4

Characteristics of individuals will be assessed in predefined time windows around the date of the first recorded prescription of immunoglobulins (index date) during the study period. For primary care data sources, a washout period of 180 days will be applied. Characteristics will be described for each prespecified immunoglobulin brand by means of large-scale characterisation and prespecified patient-level characteristics based on OMOP CDM mapped data using the *CohortCharacteristics* (<https://github.com/darwin-eu/CohortCharacteristics>) and *DrugUtilisation* (<https://github.com/darwin-eu/DrugUtilisation>) R packages, developed by DARWIN EU®.

Characteristics of interest will be reported as counts and proportions for categorical variables and as minimum, q25, median, q75, and maximum for continuous variables. Demographic characteristics, including age and sex, will be assessed at the date of first recorded prescription of immunoglobulins (index date) during the study period. Characterisation of prespecified indications for use will be assessed any time prior to 7 days after the index date, 30 days prior to 7 days after the index date, and 7 days prior to 7 days after the index date. Large-scale characterisation of comorbidities prior to immunoglobulin treatment will be assessed 30 days prior to the index date, 1 year prior to the index date, and any time prior to the index date. Characterisation of prespecified common infections and prespecified antibiotics treatment among immunoglobulin initiators will be assessed up to 30 days post-index and up to 365 days post-index.

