## 8.6. Variables

### 8.6.1. Exposure

For *objective 1*, the primary exposure is defined as a prescription or dispensing record of a prespecified immunoglobulin drug (ingredient level). For *objective 2*, prescriptions of all prespecified immunoglobulin brands of an individual during the study period will be included. For *objectives 3 and 4*, the prescription or dispensing record of prespecified immunoglobulin brands represents the first recorded prescription in the study period and individuals from primary care data sources were required to have no prior immunoglobulin use in the 180 days prior the index date.

To define treatment episodes, sequential prescriptions will be grouped into drug eras, allowing a maximum gap of 30 days between the end of one prescription and the start of the next. More details about the definition of a treatment episode are provided in [Section 8.8.3](#).

The preliminary concept sets used for the identification of exposures are described in [Annex IV](#). These codes will be refined during the study execution following the DARWIN EU® phenotyping standard processes, which involve the review of code lists, and the review of phenotypes after their execution in the participating data sources. Final concept sets will be defined following input from EMA.

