### Limitations

The study will be informed by routinely collected healthcare data, which introduces several important considerations that may influence the interpretation of the findings.

The study will include data from three European countries. As such, the results reflect only the populations captured within these data sources and may not be generalisable to other countries or healthcare systems.

Electronic health records are primarily designed for clinical purposes rather than research, and as such, may contain incomplete, inconsistent, or variably recorded information. Therefore, the documentation of comorbidities, necessary for patient-level characterisation, may vary across data sources. The actual clinical indication for prescribing immunoglobulins is not directly recorded in the data sources. Instead, proxy measures based on diagnosis codes around the time of the first treatment during the study period are used. Consequently, the estimation of potential indications may be incomplete or imprecise as this might not be recorded in all patients. To minimise incompleteness, different time windows around the immunoglobulin prescription date will be applied to assess the indication of use.

Additionally, a recorded prescription does not guarantee that the medication was dispensed or consumed, therefore assumptions of actual use have been made. Furthermore, the type of health care setting may affect the prevalence of prescriptions of specific immunoglobulin types, e.g., intravenous immunoglobulins are predominantly administered in a hospital setting and not in primary care. The general study population which will be included to estimate the prevalence of immunoglobulin use may also be affected by the type of health care setting and the definition of the observation period by each data source. Primary care data sources generally encompass a broader cohort of individuals, observed from registration until deregistration (CPRD GOLD) or from first to last recorded event (IQVIA DA Germany), while the hospital data source (CDW Bordeaux) comprises individuals requiring inpatient care which are observed from their first to last visit.

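### Cumulative dose in objective 3 charges a daily dose to every bridged gap day, which contradicts its own definition as total dose taken and overstates dose for intermittently given product

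*Protocol*

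**What the plan says.** Section 8.6.1 of the protocol groups prescriptions into eras, "allowing a maximum gap of 30 days between the end of one prescription and the start of the next". Section 8.8.3 (Objective 3, Drug exposure calculations) repeats the rule: "two drug eras will be merged into one continuous drug era if the distance in days between end of the first era" and the start of the second is at most 30 days. Record length is taken from the OMOP drug exposure table, "using the recorded start and end date of the exposure".

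For the days between joined records the protocol chooses: "The time between the two joined eras will be considered as exposed by the first era", with a pointer to the first row of Figure 4. That row sets the dose in the gap to d1 and the cumulative dose to d1·(x1+x12)+d2·x2. Figure 4 also lists two rows, 'zero' and 'join', in which the gap carries no dose; neither is selected.

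Cumulative dose is then defined: "The cumulative dose is the sum of defined daily doses (DDDs) multiplied by the number of days exposed to each dose", which the sentence explains as "the total dose taken throughout the exposures considered in the time-window reported per prespecified immunoglobulin brand".

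Where two records overlap, the overlapping days count for the earlier record only. If both start on the same date, the days count for both. Cumulative dose is reported per brand, with the three data sources side by side, in mock Table 3 of section 8.8.4.

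**The concern.** The gap rule and the definition describe different quantities. Charging d1 to the gap is sensible for a medicine taken every day, where a short gap probably reflects late refilling. The products here are almost all injections, injectable solutions or prefilled syringes (Annex IV, Table S4). The limitations section adds that "intravenous immunoglobulins are predominantly administered in a hospital setting and not in primary care", and one of the three sources is a hospital. If such a product is given on separate days with intervals in between, the term d1·x12 is dose that nobody recorded.

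Cumulative dose is a named part of objective 3. The excess depends on how many days each source stores per administration. Table 3 could therefore show differences in dose between sources or between brands that come from the joining rule and not from use. The limitations section does not mention this, and section 8.8.3 withholds only treatment duration, not dose, where duration cannot be calculated.

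**Working it through.** The protocol states no figure for this effect, so there is none to reproduce. The check applies its own formula.

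**From the protocol.** Maximum bridged gap: 30 days (sections 8.6.1 and 8.8.3). Cumulative dose under 'first': d1·(x1+x12)+d2·x2. Cumulative dose under 'zero' and 'join': d1·x1+d2·x2. Cumulative time under 'first' and 'zero': x1+x12+x2; under 'join': x1+x2.

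**Assumed, not in the documents.** Record length r (days), interval k between successive starts (days), number of records n, the same daily dose d for each record, and d equal to the amount actually recorded per day.

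**Excess for two records.** 'First' minus 'zero' is d1·x12. It is zero only if there is no gap or no dose.

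**Extension to n equal records.**
- 'First': d·[(n−1)·k + r]
- Recorded dose ('zero' or 'join'): d·n·r
- Factor: [(n−1)·k + r] / (n·r)

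For n=2, r=1, k=28 this gives 29 against 2, as Figure 4 does with x1=x2=1 and x12=27.

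| r | k | n | Calculation | Factor |
|---|---|---|---|---|
| 1 | 28 | 2 | 29/2 | 14.5 |
| 1 | 28 | 6 | 141/6 | 23.5 |
| 1 | 28 | 13 | 337/13 | 25.9 |
| 1 | 21 | 8 | 148/8 | 18.5 |
| 1 | 7 | 26 | 176/26 | 6.8 |
| 5 | 28 | 6 | 145/30 | 4.8 |
| 7 | 28 | 6 | 147/42 | 3.5 |
| 14 | 28 | 6 | 154/84 | 1.8 |
| 28 | 28 | 6 | 168/168 | 1.0 |

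For a single record (n=1) the factor is r/r = 1.0. It is also 1.0 where records lie too far apart to be joined.

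**Limit of the rule.** With one-day records and many administrations the factor tends to k. A permitted distance of 30 days means k=30 or k=31, depending on whether it leaves 29 or 30 gap days, so the rule itself allows about 30.

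**Overlap.** If a later record starts o days before the earlier one ends, the 'first' overlap rule drops d2·o from the total. Two one-day records can overlap only by starting on the same date, and those are already counted as both. The loss therefore arises only for multi-day records with different start dates.

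**The case against.** The strongest reply is that the large factors rest on assumed inputs. No section says that records last one day, and none gives an interval or a number of administrations. Two of the three sources hold outpatient records, where a prescription may already cover the interval; the factor is then 1.0. Brands used once would show no effect at all. This stands, and it limits what can be said about size. It does not remove the conflict between the chosen gap dose and the definition.

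A second reply is that the consequence is contained. Cumulative dose is one of four measures in Table 3. Initial dose and number of exposures do not depend on the gap rule, exposed time is the same under 'first' and 'zero', and the study is descriptive with no pooling. This also stands. It narrows the damage to one output, though one that an objective names.

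Three stronger readings are tempting and are not supported:

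- **About 25-fold as a finding or a ceiling.** It is one scenario (one-day records every 28 days, about 13 of them), and the rule allows about 30.
- **DDD times days measures only time.** The text does say DDD, which can be read as a fixed reference amount. But Figure 4 gives each record its own d1 and d2, which points to the record's own daily dose. On the fixed-amount reading the factors above would not follow, because d times the span is not a known multiple of the amount given. Only a wording clarification is warranted.
- **The overlap rule always discards the second dose.** The protocol expressly counts same-date starts as both.

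**Conclusion.** The point holds. As written, section 8.8.3 adds the preceding record's daily dose to every bridged gap day and then labels the sum the total dose taken. No other part of the protocol corrects this. Wherever a gap is bridged for product not used daily, cumulative dose is too high.

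The mechanism is certain; the size is not. Under the assumptions listed, the factor runs from 1.0 (single records, or records that span the interval) through about 7 (weekly one-day records) to between 14.5 and about 26 (2 to 13 one-day records every 28 days). These figures illustrate the range and do not estimate what the three sources will show. A reader might infer that between-source or between-brand contrasts in Table 3 will be artefacts. The documents support only that they could be, depending on how each source records duration.

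**What to change.** - **Gap dose.** For cumulative dose, select the 'zero' row of Figure 4: gap dose 0, cumulative dose d1·x1+d2·x2. The factor is then 1.0 for every interval and record length in the illustration. Exposed time stays x1+x12+x2, so duration results do not change; 'join' would give the same dose but would shorten exposed time to x1+x2.
- **Meaning of d.** State that d is the recorded daily dose of each record, not a fixed defined daily dose.
- **Overlap.** For multi-day records that overlap with different start dates, say that the present rule drops the later record's dose on the shared days, and reconcile this with the definition of total dose. Same-date starts need no change.

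The cost of the first change is a sentence in section 8.8.3 and a setting in the analysis code; the second is wording only. The third needs a decision on the overlap setting and a sentence to record it. Rebuilding dose from quantity times strength would be a larger change and is not needed to resolve this point.

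### Cumulative dose charges bridged gap days at the first exposure's daily dose, contradicting its own definition as dose taken; the bias is only upward and its size depends on record lengths the protocol does not give

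*Protocol*

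**What the plan says.** Section 8.6.1 groups successive prescriptions into drug eras, "allowing a maximum gap of 30 days between the end of one prescription and the start of the next". Section 8.8.3, under drug exposure calculations, repeats the 30-day limit and settles how the gap is treated: "The time between the two joined eras will be considered as exposed by the first era", with reference to the first row of Figure 4. That row sets the dose between exposures to d1, cumulative dose to d1·(x1 + x12) + d2·x2, and cumulative time to x1 + x12 + x2.

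The next sentence defines the quantity: "The cumulative dose is the sum of defined daily doses (DDDs) multiplied by the number of days exposed to each dose", glossed as "the total dose taken throughout the exposures considered in the time-window reported per prespecified immunoglobulin brand".

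Record lengths come from the data: "the estimated duration of use will be retrieved from the drug exposure table in the OMOP CDM, using the recorded start and end date" of each exposure. Cumulative dose is a named output of objective 3, given per brand in section 8.8.3 and shown per brand and per data source in mock Table 3 of section 8.8.4.

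**The concern.** The interval x12 is by construction time that no record covers. Charging it at d1 adds drug that no record supports, so the formula and the stated meaning of the result cannot both stand. This is a rule that the protocol itself fixes, not a detail left for a later analysis plan.

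The consequence depends on how records are dated. If a record's start and end dates span the whole dosing interval, there is no gap and nothing is added. If an administration is dated to one day or a few days, most of the interval to the next one becomes gap and is charged in full. Cumulative dose then follows elapsed calendar time more than the amount recorded. Section 9 notes that intravenous products are mainly given in hospital, and Table 1 in section 8.4 has the hospital source contributing to all objectives alongside two outpatient sources. Record lengths could therefore differ between the columns of Table 3, although the protocol does not say that they do.

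Nothing elsewhere would reveal the problem. Section 9 does not mention it, and item 10.8 of the ENCePP checklist marks sensitivity analyses as not applicable. Section 8.8.3 allows treatment duration to be withheld where it cannot be calculated, but that does not address dose added for gaps.

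**Working it through.** The protocol gives no numerical result to reproduce, so the first step checks the formulas.

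**Step 1. Size of the added term (Figure 4).** 'First' gives d1·(x1 + x12) + d2·x2 and 'zero' gives d1·x1 + d2·x2. The difference is d1·x12. With arbitrary values d1 = 2, d2 = 3, x1 = 5, x12 = 10, x2 = 7, 'first' = 2·15 + 3·7 = 51 and 'zero' = 2·5 + 3·7 = 31. The excess is 20 = d1·x12. Cumulative time is 22 days under both.

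**Step 2. General ratio.** Take n records of L days each, starting every T days at a common daily dose, with uncovered gap g = T − L short enough to be merged. Then

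ratio of 'first' to recorded dose = [nL + (n − 1)g] / (nL), approaching 1 + g/L as n grows.

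Only the 30-day limit comes from the protocol. The values of n, L and T below are assumptions, varied to show the range.

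**Step 3. Effect of record length (T = 28, n = 13).**

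| Record length L | Gap g | Ratio |
|---|---|---|
| 28 days | 0 | 364/364 = 1.0 |
| 14 days | 14 | (182 + 168)/182 = 1.9 |
| 7 days | 21 | (91 + 252)/91 = 3.8 |
| 2 days | 26 | (26 + 312)/26 = 13.0 |
| 1 day | 27 | (13 + 324)/13 = 25.9 |

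**Step 4. One-day records, by interval and number.** Here the ratio is [(n − 1)T + 1]/n.

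- Two records: T = 7 gives 8/2 = 4.0; T = 30 gives 31/2 = 15.5; T = 31 gives 32/2 = 16.0.
- Roughly a year: T = 7, n = 49 gives 337/49 = 6.9; T = 21, n = 17 gives 337/17 = 19.8; T = 28, n = 13 gives 337/13 = 25.9; T = 30, n = 12 gives 331/12 = 27.6; T = 31, n = 12 gives 342/12 = 28.5.
- Limit for many records at the longest bridged gap: 30 if 29 days are uncovered, 31 if 30 days are uncovered.

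**Step 5. Where merging stops.** The 30-day distance can mean uncovered days or the difference between the end date and the next start date. For one-day records the longest merged interval is T = 31 on the first reading and T = 30 on the second. One day beyond it, nothing is merged, no gap dose is added and the ratio falls to 1.0.

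**Step 6. Loss of contrast.** Suppose each one-day record carries 40 g and d is that full amount. Thirteen records at 28-day intervals are 13·40 = 520 g; forty-nine at 7-day intervals are 49·40 = 1,960 g. Under 'first' both become 337·40 = 13,480 g.

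**The case against.** The best defence has four parts.

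- **No size can be read from the plan.** The protocol gives no dosing interval, record length or number of records, and it takes durations from the data. This stands. A reader might infer that cumulative dose will be inflated by some fixed multiple, such as 7- to 29-fold, but that needs one-day records over about a year, and its top end also needs the gap counted as uncovered days. The documents establish neither. Two of the three sources are outpatient prescribing records, where longer durations are possible.
- **The dose is framed through defined daily doses.** If d is a standard daily amount rather than the recorded one, the whole product is an imputation, and removing gap dose would still not return the amount given. This stands too, and it shapes the fix: 'zero' alone is not safe under every meaning of d.
- **Little is contrasted formally.** Sources are analysed separately, there is no meta-analysis, and Table 3 also shows initial dose, number of exposures and days exposed. So it would go too far to call differences between brands or sources artefacts; they may partly be so.
- **The bridged era may be what is meant by the exposures considered.** Bridging is a reasonable convention for duration. It does not make uncovered days into dose taken, and 'zero' gives the same cumulative time without the added dose.

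None of this reconciles the formula with the definition beside it.

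**Conclusion.** The rule is wrong as written. With a bridged gap of more than zero days and a non-zero d1, the formula exceeds the quantity that the paragraph says it measures, and the bias can only be upward. That conclusion needs no assumption about the data.

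The size is conditional. It runs from 1.0, when records cover the interval or the gap is too long to merge, to about 31. For one-day records it is about 4 to 16 with two records and about 7 to 28 over roughly a year. Even 14-day records at 28-day intervals nearly double the dose. These figures assume equal record lengths, equal daily doses and regular intervals. If record length differs by source or brand, side-by-side cumulative doses in Table 3 may partly reflect how administrations are dated.

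**What to change.** In section 8.8.3, define cumulative dose as the sum of the recorded amounts of the records in the episode. Alternatively, where the daily dose is derived from recorded amount and duration, use the 'zero' row of Figure 4 for dose. State which meaning of daily dose applies, since the present wording refers to defined daily doses. Keep gap days in treatment duration only; cumulative time stays at x1 + x12 + x2 under 'zero'. State also whether the 30-day distance counts uncovered days or a date difference.

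The cost is a short text change and the matching analysis setting, with no new data. Reported cumulative doses will be smaller than under the present rule wherever gaps are bridged.
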